9.2.4.7. Preexisting Medical Conditions

A preexisting medical condition should be recorded as an AE only if the frequency, severity, or character of the condition worsens during the study. When recording such events on the AE form, it is important to convey the concept that the preexisting condition has changed by including applicable descriptors (e.g., "more frequent headaches").

9.2.4.8. Hospitalization or Prolonged Hospitalization

The following hospitalizations are not considered SAEs in this clinical trial:

- Admissions per protocol for a planned medical/surgical procedure. Planned hospital admissions or planned surgical procedures for an illness or disease that existed before the patient was enrolled in the trial or before study drug was given are not to be considered

AEs, unless they occur at a time other than the planned date for a reason such as a worsening of the underlying disease/illness/symptoms.

- Routine health assessment requiring admission for baseline/trending of health status (e.g., routine colonoscopy).
- Medical/surgical admission for purpose other than remedying ill health state and was planned prior to entry into the study. Appropriate documentation is required in these cases.

Admission encountered for another life circumstance that carries no bearing on health status and requires no medical/surgical intervention (e.g., lack of housing, economic inadequacy, care-giver respite, family circumstances, administrative).

9.2.4.9. Pregnancy Exposure and Birth Events Reporting

Andexanet is not expected to have reproductive or developmental toxicity based on the following:

- Andexanet is intended for single-dose administration and, therefore, has limited potential for reproductive or developmental toxicity.
- Andexanet is a biotechnology-derived protein that is a modification of an endogenous protein in the coagulation cascade (FXa).
- Andexanet has a very short $t_{1/2}$ (1–2 hour effective $t_{1/2}$).
- Andexanet was designed as a universal antidote for FXa inhibitors, which are prescribed primarily in elderly patient populations that are not of reproductive capacity.

However, it is recommended that women of childbearing potential must use 2 medically acceptable methods of contraception, at least 1 of which must be a barrier method (e.g., non-hormone containing intra-uterine device plus condom, spermicidal gel plus condom), through at least 1 month following study drug dose.

Additionally, men with sexual partners of childbearing potential must use 2 acceptable methods of contraception, at least 1 of which must be a barrier method (e.g., spermicidal gel plus condom), for the entire duration of the study and for at least 1 month following study-drug; and men must refrain from attempting to father a child or donating sperm in the month following the study-drug.

Periodic abstinence (e.g., calendar, ovulation, symptothermal, post-ovulation methods) and withdrawal are not acceptable methods of contraception.

If a female study patient becomes pregnant or a female partner of a male study patient suspects she is pregnant, the Investigator should be informed immediately. Portola must, in turn, also be notified by the Investigator immediately by completing a Pregnancy Form. If a female partner of

a male study patient is pregnant or suspects she is pregnant, the male patient will be advised by the study Investigator to have his pregnant partner inform her treating physician immediately. The pregnancy must be followed up through delivery or other fetal outcome and information reported on a Pregnancy Follow-up form. For any abnormal fetal outcome (including congenital anomaly or birth defect, spontaneous or therapeutic abortion, still birth, pre-mature birth, or other outcome other than live normal birth), the Investigator should promptly report the abnormal fetal outcome to the Sponsor on an SAE form.

10.0 STUDY ASSESSMENTS

Assessments, testing and treatment schedules are detailed in [Appendix A](#). No reference to timing or frequency is described below.

10.1. Baseline Assessments

10.1.1. Informed consent

An IRB/EC approved informed consent will be administered prior to performing study specific procedures or assessments. Administering informed consent is a process and will be documented in source documents. The current IRB/EC version of the consent will be used.

10.1.2. Demographics

Demographics will record the age, sex, race and ethnicity of patients. Race will be recorded (American Indian or Alaska Native, Asian, Black or African American, Native Hawaiian or Other Pacific, White), and ethnicity will be recorded as Hispanic or Latino or Non-Hispanic or Latino.

10.1.3. Medical History

Patients will have a detailed medical history completed as part of baseline assessments. Diagnosis, year of onset and status will be reported. Status will consist of an end date or documentation as ongoing for the condition. Diagnosis should be documented and not signs and symptoms. Events with current treatment will have the treatment recorded in concomitant medications and therapies.

10.1.4. Prior and Concomitant Medications

Patients will be asked about their current physician prescribed medications, over the counter medications and any herbal or nutritional supplements. The generic name is preferred for Electronic Data Capture (EDC) entry. The dose, posology, frequency, start and stop dates and the diagnosis for use will be recorded.

10.1.5. Anticoagulant Dose or Plasma Level

Patients will be asked about the brand, dose and time of last dose of their anticoagulant. For patients who received the last dose of FXa inhibitor more than 15 hours (or an unknown time) prior to start of surgery, a local anti-fXa activity level may be obtained to allow enrollment of patients with >100 ng/mL levels. See Section [10.2.1](#) below on details for this local testing.

10.1.6. American Society of Anesthesiologists Physical Status Classification (ASA PS)

The American Society of Anesthesiologist Physical Status Classification is used to evaluate and describe the general health of patients prior to use of anesthetics or prior to surgery. The ASA PS consists of 6 categories to describe a patient's physical status ([Appendix F](#)). It will be used to

describe the population enrolled in the trial. It is not an assessment of operative risk, and will not be repeated during the study.

10.1.7. Eligibility Assessment

Following completion of assessments and screening testing, the investigator will determine eligibility of the patient by comparing results to inclusion and exclusion criteria. Note: it is Portola Pharmaceuticals Policy not to grant exceptions or waivers for inclusion and exclusion criteria.

10.1.8. Patient Identification Numbers

Patients will be considered to be in Screening once they have signed the ICF. At this time, patients will be assigned a patient identification number. Patients will be considered to have enrolled in the study once they have signed informed consent and met the inclusion and exclusion criteria.

10.2. Central Laboratory Testing

Details on the collection, processing, storage, and shipment of samples are contained in the Laboratory Manual.

10.2.1. Anti-fXa Activity

Anti-fXa activity will be measured using plasma samples to assess the ability of andexanet to reverse the anticoagulant effect of FXa inhibitors. Anti-fXa activity will be measured by a modified chromogenic assay. These assays will be performed at a Central Laboratory.

Local laboratory anti-fXa activity testing may be utilized additionally by sites to ascertain eligibility (>100 ng/ml) if the time of last dose of FXa inhibitor is greater than 15 hours (or unknown). Local laboratory testing post-andexanet administration should be done with caution due to potential invalidity of local lab results from excessive sample dilution.

10.2.2. Thrombin Generation

Thrombin generation will be measured using plasma samples to assess the ability of andexanet to reverse the anticoagulant effect of FXa inhibitors. Thrombin generation will be measured using a tissue factor (TF)-initiated TG assay. This assay will be performed at a Central Laboratory. Five parameters related to TG are measured: endogenous thrombin potential (ETP), peak height, time to peak height, lag time and velocity index. Endogenous thrombin potential is prospectively identified as the primary measure for TG.

10.2.3. Tissue Factor Pathway Inhibitor

The TFPI activity will be measured using plasma samples in a Central Laboratory using a validated assay. The TFPI functional activity will be determined using a commercial kit. The assay measures FXa chromogenic activity following FX activation by factor VIIa/TF added to

the plasma. The TFPI activity is quantified by using a TFPI standard with U/mL as the readout. Binding of andexanet to TFPI will reduce the TFPI activity readout.

10.2.4. Anti-IIa Activity

Anti-IIa activity levels will be measured in patients taking enoxaparin using plasma samples. Anti-IIa activity will be measured using a modified chromogenic assay. Anti-IIa activity results will be performed in a Central Laboratory.

10.2.5. Antibody Testing

Determination of the possible presence of antibodies to FX (human) and FXa (human) will be done at specific time points (see [Appendix A](#)) using the modified Bethesda assay. Antibodies against andexanet and HCPs will be assessed using standard immunogenicity assays.

For any sample that is positive for antibodies against andexanet, the potential for nAb activity will be further assessed by measuring the functional activity of andexanet in plasma. These tests will be performed by a Central Laboratory.

10.3. Safety Assessments (other than Adverse Events)

10.3.1. Vital Signs

Vital signs include temperature (°C), systolic blood pressure (SBP) (mmHg), diastolic blood pressure (mmHg), heart rate (beats per minute), and respiratory rate (respirations per minute).

10.3.2. Physical Examination

A physical examination will be performed on all patients at various time points before and after the surgical procedure. The examination will include, at a minimum, any component relevant to the indication for surgery (e.g., abdominal examination for appendicitis, hip examination for hip fracture, neurologic examination for spinal cord compression) and an assessment of the surgical incision site (post-operative only).

10.3.3. Weight

Patient weight will be recorded in kg according to the schedule of assessments in [Appendix A](#).

10.3.4. Clinical Laboratory Testing

Blood specimens for routine chemistry and hematology will be obtained at selected time points (see [Appendix A](#)).

The following assays will be performed at the Local Laboratory:

- Hematology: hemoglobin, hematocrit, white blood cell (WBC) count, platelet count, WBC differential
- Coagulation: prothrombin time reported as the INR

- Serum Chemistry: sodium, potassium, chloride, carbon dioxide (bicarbonate), glucose, blood urea nitrogen, creatinine, aspartate aminotransferase, alanine aminotransferase, alkaline phosphatase, and total, direct, and indirect bilirubin
- Serum or urine pregnancy test (in women of child bearing potential; see [Appendix D](#))

10.3.5. Optional Local Laboratory Testing of Anti-fXa Levels

Local laboratories may perform tests to evaluate anti-fXa activity to address inclusion criteria. Further details and guidance on the conduct of local laboratory anti-fXa assays can be found in the Laboratory Manual for ANNEXA-S. Investigators are discouraged from evaluating anti-fXa activity with local assays after the administration of andexanet, due to the known inaccuracy of post-andexanet results caused by the large sample dilutions associated with unmodified commercial anti-fXa assays; however, if such testing is deemed necessary, it is strongly recommended that the procedures outlined in the Laboratory Manual be followed.

10.4. Intraoperative and Hospitalization Assessments

10.4.1. Surgical Intervention

All patients entering the trial are required to have an urgent need for surgical intervention. Institutional or procedural consents should be administered for the surgical intervention in accordance with local requirements and in addition to the study specific informed consent.

- The start of surgery is the initial incision.
- The end of surgery is final skin closure.

10.4.2. Intraoperative Blood Loss

Investigators will report blood loss during surgery for each patient. Blood loss will be reported as an estimate of blood loss in milliliters. Blood loss will be reported at the end of surgery. It is an intraoperative assessment and will not be updated for post-closure blood loss.

10.4.3. Assessment of Intraoperative Hemostasis

Intraoperative hemostasis will be captured as an investigator assessment. Categories for assessment are provide in [Table 3](#) (Section 11.5.1).

10.4.4. Blood Products and Hemostatic Treatments

Blood products and hemostatic treatments employed as treatment prior to, during and postoperatively will be recorded. The product (generic), dose, route of administration, date and time of use will be recorded along with the reason for use.

10.4.5. Bleeding-related Diagnostic and Therapeutic Procedures

Any diagnostic and/or therapeutic procedures employed prior to, during and postoperatively will be recorded. For diagnostic procedures, the procedure, date, time, results and relevant units or description of results will be captured. Therapeutic procedures will be captured and concomitant medications/treatments with date, time, and posology (if applicable).

As a concomitant treatment, Investigators will record the product (generic name), date, time, indication and posology of colloid or crystalloid treatments used to support hemodynamic status.

10.4.6. Record Hours in Hospital Care Units

Investigators will record the date and time of entry into each care unit of the hospital. The date and time of entry and exit for each unit will be reported. This will be locally variable, but categories should be reconciled to the standards below:

- Emergency Department (ED): a unit dedicated to medical and surgical patients in need of immediate care.
- Intensive Care/Critical Care Department (ICU): a specialty medical unit for patients that are seriously ill are maintained under constant medical observation.
- Operating Room (OR): the room where the surgical procedure actually takes place.
- Post-anesthesia Care Unit (PACU): a specialty unit for providing post-anesthesia care for patients recovering from anesthesia.
- General Hospital Department or General Surgical Department: Covers a wide range of types of surgery and procedures on patients.

10.5. End of Study Assessments

Patients will have their survival status reported on the Day 30 or End of Study visit. This assessment will record the patient's status as alive or provide the date, time and cause of death. Note: see Section 9.0 for AEs reported for all deaths.

11.0 STATISTICAL CONSIDERATIONS AND DATA ANALYSIS

The study objectives and study design are described in Sections [2.0](#) and [3.1](#), respectively. The information in this section is a summary of the planned statistical analyses. Further details will be provided in the detailed Statistical Analysis Plan.

11.1. General Considerations

Statistical summaries will be performed using SAS Version 9.4 (SAS Institute, Inc., Cary, NC, USA) or higher. Additional software may be used for the production of graphics and for statistical methodology not available in SAS.

All hypothesis tests will be 2-sided and reported at the 0.05 significance level. All confidence intervals (CIs) will be 2-sided and reported at the 95% confidence level.

11.2. Randomization

This is a prospective, open-label study with a single treatment arm. Consequently, there is no randomization.

11.3. Analysis Populations

11.3.1. Enrolled Population

The enrolled population will consist of all patients enrolled (signed informed consent and met inclusion/exclusion criteria) into the study irrespective of whether they received andexanet or not.

11.3.2. Safety Analysis Population

The safety analysis population will consist of all patients enrolled and treated with any amount of andexanet.

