11.7. Safety Endpoints and Summaries

Safety will be assessed by examining the following endpoints and analyzed in the Safety Analysis Population:

- AEs (including SAEs), vital signs, physical examinations, and clinical laboratory measurements.
- TEs within 30 days of enrollment, including those suspected and confirmed by adjudication.
- Centrally-adjudicated deaths within 30 days of enrollment, including all-cause mortality and cardiovascular mortality.
- Antibodies to FX, FXa, andexanet, and HCPs.

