4.0 SELECTION OF STUDY POPULATION AND CRITERIA FOR WITHDRAWAL

4.1. Inclusion Criteria

All of the following criteria must be met for the patient to be eligible to participate in the study:

1. Either the patient or his or her medical proxy (or legal designee) has given written informed consent prior to Screening.
2. Age ≥ 18 and < 85 .
3. Requires urgent surgical intervention that must occur within 12 hours of clinical presentation, for which reversal of anti-fXa activity is judged necessary.
4. Received 1 of the following FXa inhibitors within 15 hours prior to start of surgery: apixaban, rivaroxaban, edoxaban, or enoxaparin (dose of enoxaparin ≥ 1 mg/kg/d), OR if a local anti-fXa activity level obtained within 2 hours prior to consent is > 100 ng/mL (> 0.5 IU/mL for enoxaparin), the patient may be enrolled, irrespective of the time of the last dose.
5. Have a negative pregnancy test documented prior to enrollment (for women of childbearing potential).
6. Willingness to use medically acceptable methods of contraception through 30 days following study drug dose (for female and male patients who are fertile).

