5.1. Screening Period

5.1.1. Subject Identification Numbers

Patients will be considered to be in Screening once they have signed the ICF. At this time, patients will be assigned a patient identification number. Patients will be considered to have enrolled in the study once they have met the inclusion and exclusion criteria.

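### Read literally, the Safety Analysis Population leaves out treated patients later found ineligible, because being enrolled is defined as having met the eligibility criteria

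*Protocol*

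**What the plan says.** Three definitions in Amendment 1 have to be read together.

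- Section 11.3.2 sets the safety set as "all patients enrolled and treated with any amount of andexanet".
- Section 11.3.1, directly above it, says who is enrolled: "all patients enrolled (signed informed consent and met inclusion/exclusion criteria) into the study irrespective of whether they received andexanet or not".
- Section 10.1.8 says the same in operational terms: "Patients will be considered to have enrolled in the study once they have signed informed consent and met the inclusion and exclusion criteria".

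Section 11.7 then assigns every safety endpoint to that set: "Safety will be assessed by examining the following endpoints and analyzed in the Safety Analysis Population". The list covers AEs and SAEs, vital signs, examinations, laboratory results, thrombotic events (TEs), adjudicated deaths and antibodies.

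Section 10.1.7 has the investigator determine eligibility after screening, and adds that "it is Portola Pharmaceuticals Policy not to grant exceptions or waivers for inclusion and exclusion criteria". The original protocol already tied enrolment to the criteria in its Section 5.1.1: "Patients will be considered to have enrolled in the study once they have met the inclusion and exclusion criteria".

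**The concern.** A safety set is normally defined by exposure. Here it is defined by exposure and enrolment, and enrolment carries an eligibility condition. An exposed patient who turns out to have breached a criterion would then fall outside the safety tables.

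The setting makes late discovery realistic. Appendix A puts consent, medical history, the eligibility decision and drug preparation into one window, from 2 hours to 45 minutes before surgery. Section 13.2 allows proxy or emergency consent, so a history may be incomplete at that point. The no-waiver policy rules out knowing exceptions but not errors discovered afterwards.

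At stake is a possible selection effect on the safety rates. Section 3.5 of the original protocol explains that patients with a recent TE, a history of hypercoagulable states or recent procoagulant products are kept out because their TE risk is much greater. If some of those treated in error belong to these groups, the omitted patients would be informative about the trial's adverse event of special interest. The study has a single arm (Section 11.2), so no control group would show a parallel effect.

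**Working it through.** **Step 1: follow the definitions.**

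1. Safety set = enrolled and treated (11.3.2).
2. Enrolled = consent signed and criteria met (11.3.1, 10.1.8).
3. So safety set = consent signed, criteria met and treated.
4. A treated patient who did not meet a criterion fails the second condition.
5. All Section 11.7 endpoints are analysed in this set, and no section at hand puts such a patient back.

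**Step 2: can a correctly screened patient fail later?** Inclusion criterion 4 in the original protocol (Section 4.1) reads "Received 1 of the following FXa inhibitors within 15 hours prior to start of surgery". Amendment 1 Section 10.1.5 also counts the 15 hours back from the start of surgery. Appendix A gives the bolus before surgery. A delayed incision can therefore leave a patient who has already been dosed outside the limit.

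**Step 3: the plan's own safety-related figure.** Section 11.6 states a 78% to 84% chance of seeing an event with a 1% rate in 150 to 180 patients.

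- 1 − 0.99^150 = 77.9%
- 1 − 0.99^180 = 83.6%

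The figure reproduces and is not in dispute.

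**Step 4: illustration of size.** The documents do not give the number of ineligible treated patients, so the following are assumptions:

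- N = 200 treated, taken from the planned enrolment of about 200 in Section 11.6.
- Ineligible share f of 2%, 5% or 10%, that is k = 4, 10 or 20 patients.
- TE rate r = 9.7% among eligible patients. Original Section 3.5 gives this rate for the earlier study in acute major bleeding, a different population.
- Ineligible patients have m = 1, 2 or 3 times that rate.

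Formulas: rate in the safety set read literally = r; all-treated rate = [(N − k)·r + k·m·r] / N; events left out = k·m·r; chance of at least one 1%-rate event = 1 − 0.99^(N − k).

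Worked case, k = 10 and m = 2: (190 × 0.097 + 10 × 0.194) / 200 = 10.2%.

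| k | m | Literal safety set | All treated | Events left out |
|---|---|---|---|---|
| 4 | 1 | 9.7% | 9.7% | 0.39 |
| 4 | 2 | 9.7% | 9.9% | 0.78 |
| 4 | 3 | 9.7% | 10.1% | 1.16 |
| 10 | 1 | 9.7% | 9.7% | 0.97 |
| 10 | 2 | 9.7% | 10.2% | 1.94 |
| 10 | 3 | 9.7% | 10.7% | 2.91 |
| 20 | 1 | 9.7% | 9.7% | 1.94 |
| 20 | 2 | 9.7% | 10.7% | 3.88 |
| 20 | 3 | 9.7% | 11.6% | 5.82 |

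The chance of seeing a 1%-rate event is 86.6% with all 200 patients, and 86.1%, 85.2% or 83.6% after dropping 4, 10 or 20.

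For scale, the 95% half-width at 9.7% and n = 200 is 1.96 × √(0.097 × 0.903 / 200) = 4.1 percentage points.

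**The case against.** The best reply is that enrolled is a status fixed at entry. Section 10.1.8 makes it start at a moment, Section 10.1.7 has the investigator decide eligibility after screening, and nothing un-enrols a patient later. Section 11.6 supports this. It counts cancelled surgeries as attrition from the roughly 200 enrolled, yet a patient who never reaches incision cannot literally satisfy a criterion timed to incision. If eligibility had to be confirmed after the fact, nobody could be enrolled before the bolus. On this reading the safety set is an ordinary all-treated set and a late finding is a protocol deviation. The reading is plausible and may be what the sponsor intends. It is not written down: Section 11.3.1 says the criteria were met, not that they were judged to be met, so two analysts could build different sets.

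Three stronger inferences are tempting and do not stand.

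- *The events would be lost.* Section 9.2.1 requires reporting without reference to later eligibility findings. Sections 11.7.2 and 11.7.3 send all TEs and deaths to the adjudication committee, and Section 12.0 has that committee adjudicate for all patients and the DSMB monitor all safety data. Only membership of the summaries is in question.
- *The thrombotic-risk exclusions are the criteria most likely to be breached.* Nothing in the documents shows this. Age, predicted length of surgery, timing and prior investigational drug can be breached too, with no stated direction for TE risk. Severe sepsis is not among the groups that original Section 3.5 describes as high risk.
- *The bias has a known size.* Every input to the illustration other than the planned enrolment is assumed or borrowed.

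It can also be said that an SAP commonly settles such cases. It may, and none is at hand. But the protocol itself fixes both definitions, so an SAP would have to reinterpret them.

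**Conclusion.** The point holds as a defect in the definitions. Followed literally, Sections 10.1.8, 11.3.1 and 11.3.2 leave a treated patient later found ineligible out of the Section 11.7 summaries, and the entry-status reading that would prevent this is not stated. It cannot be concluded that the plan will certainly omit such patients.

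The effect is probably small. Under the assumed range the all-treated TE rate exceeds the tabulated one by 0 to about 1.9 percentage points, and by 0.5 to 1.0 points in the middle case of 10 ineligible patients at two to three times the risk. That is well inside the sampling error of 4.1 points. A downward bias arises only if the omitted patients have a higher event rate than the rest; at equal risk there is none. No sample size or precision figure in the plan changes.

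The population definitions are current Amendment 1 text. The criteria wording and the Section 3.5 rationale come from the original protocol, because the corresponding Amendment 1 sections are not among the pages at hand.

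**What to change.** - **Section 11.3.2:** define the Safety Analysis Population as every patient given any andexanet, regardless of whether all eligibility criteria are later found to have been met.
- **Sections 10.1.8 and 11.3.1:** define enrolled as consent plus the investigator's determination of eligibility at entry, so that a later finding does not change the status.
- **Reporting:** keep eligibility violators in the safety summaries and list them as protocol deviations.

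The cost is about one sentence in each section. Sample size, trial conduct and clinical management are unaffected. The one downside is that reported safety rates may be slightly less favourable.
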